4.3.2.3. Sensitivity analyses

Refer to Section 4.2.3.

4.3.2.4. Additional estimands

Refer to Section 4.2.4.

4.4. Exploratory Endpoints Analyses

CCI

4.5. Other Safety Analyses

Besides those pregnancy outcomes and AESIs defined in the primary endpoints in Section [4.2.1](#), the other safety data which will be recorded and reported include medically attended AEs, SAEs, SAEs due to study participation, and SAEs related to a GSK product.

The safety analyses will be based on the Maternal Full Analysis Set and Infant Full Analysis Set, with medical records data collection, unless otherwise specified.

Concomitant medications will be coded using the GSKDRUG dictionary. The number and percentage of maternal participants taking concomitant medications up to Day 42 post-delivery will be summarized. A listing will also be provided.

The number and percentage of infants taking concomitant medications/vaccinations from birth up to Day 42 post-delivery will be summarized by group. A listing will also be provided.

Listings and a subset of analysis outputs will be provided to SRT for safety monitoring. The planned outputs are shown in Section 6.3. Other outputs will be provided if deemed necessary.

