8.4.1. Time period and frequency for collecting MAE, SAE, and other safety information

All SAEs due to study participation will be collected from the signing of the ICF and/or IAF until Day 42 post-delivery or study conclusion at the time points specified in the SoA (Section 1.3).

SAEs assessed as related to study participation (e.g., protocol-mandated procedures) or related to a GSK product (non-IMP) will be recorded from the time a participant consents to participate in the study.

MAEs and SAEs for maternal participants will be collected during pregnancy until Day 42 post-delivery at the time points specified in the SoA (Section 1.3).

Table 6 Collection and reporting of safety information

Event	Visit 1 D1	Bi-annual contacts for 2 years until pregnancy	Initial Pregnancy Contact	Monthly contacts until Delivery	Delivery	Contact Day 42 post- delivery	Study Conclusion
SAEs related to study participation** or related to a GSK product							
Pregnancy outcome							
MAEs							
SAEs							
Pregnancy related AESIs							
Infant AESIs							
Infant MAEs							
Infant SAEs							

* i.e., consent obtained; D: Day, M: Month

** Any SAEs assessed as related to study participation (e.g., protocol-mandated procedures) or related to a GSK product will be recorded from the time a participant consents to participate in the study.

The shaded regions in the table indicate time period of data collection

All SAEs, AESIs and SAEs related to study participation will be recorded and reported to the sponsor or designee immediately and under no circumstance should this exceed 24 hours, as indicated in Section 10.2. The investigator will submit any updated SAE data to the sponsor within 24 hours of it being available and/or awareness.

A poststudy SAE is defined as any event that occurs outside of the SAE reporting period defined in Section 8.4.1 and Table 6.

Investigators are not obligated to actively seek information on SAEs after conclusion of the study participation. *However, if the investigator learns of any SAE, including a death, after a participant has been discharged from the study, the investigator must record it in the medical records. If the investigator considers the event to be reasonably related to study participation, the investigator must promptly notify the sponsor.*

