3. ANALYSIS SETS

Table 2 Maternal Participants

| Analysis Set | Definition / Criteria | Analyses Evaluated |
|-------------------------|---|---------------------------------------|
| Screened | All participants who were screened for eligibility. | Study Population |
| Enrolled | All maternal subjects who completed the informed consent process and signed the informed consent form and were determined eligible for study participation. Note screening failures (who never passed screening even if rescreened) are excluded from the Enrolled analysis set as they did not enter the study. | Study Population |
| Full Analysis Set (FAS) | All maternal subjects who had pregnancy defined by this study (defined in the Protocol Section 5.1). | Primary, Secondary and other analyses |

Table 3 Infant Participants

| Analysis Set | Definition / Criteria | Analyses Evaluated |
|-------------------------|--|---------------------------------------|
| Enrolled Infant | Infants live-born to the maternal set, whose parents/LARs completed the informed consent process and signed the informed consent form. | Study Population |
| Full Analysis Set (FAS) | All infant subjects in the infant set who have post-delivery/birth data. | Primary, Secondary and other analyses |

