4.5.1. Adverse Events

Safety analyses in maternal participants will include summaries by study arms of MAEs, SAEs, SAEs due to study participation, and SAEs related to a GSK product.

Safety analyses in infant participants will include summaries by study arms and gestational age at birth (≥ 37 weeks; <37 weeks; overall) of MAEs, SAEs and SAEs due to study participation.

For MAEs until Day 42 post-delivery (Mothers: conception to Day 42 post-delivery; Infants: birth to Day 42), the number and percentage of maternal or infant participants with each MAE with exact 95% CIs will be tabulated by study arms and displayed by Medical Dictionary for Regulatory Activities (MedDRA) preferred term. By-participant listings will be prepared.

For SAEs and SAEs due to study participation, the number and percentage of participants with each SAE with exact 95% CIs will be tabulated by study arms and by MedDRA preferred term. By-participant listings will be prepared.

The number and percentage of maternal (or infant) participants and maternal pregnancies (based on pregnancies instead of subject) reporting

- at least one MAE
- at least one SAE
- at least one SAEs due to study participation

from study pregnancy conceived up to Day 42 post-delivery (or from delivery up to Day 42 post-delivery for infant participants) with exact 95% CIs will be tabulated by study arms.

A summary of number and percentage of participants with any recorded adverse events by maximum severity will be produced.

A separate summary will be provided for study intervention (administrated from previous RSV MAT studies) related MAEs and SAEs, respectively. A study intervention-related MAE (or SAE) is defined as a MAE (or SAE) for which the investigator classifies the possible relationship to study intervention from previous RSV MAT studies as “Yes”. A worst-case scenario approach will be taken to handle missing relatedness data, i.e. the summary table will include events with the relationship to study intervention as ‘Yes’ or missing.

Summaries of life-threatening and fatal SAEs by PT will also be created.

By participant listings of MAEs, SAEs and SAEs due to study participation will be prepared.

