6.2. Appendix 2 Data Derivations Rule

6.2.1. Study Period

The study period starts from the date of start of any pregnancy conceived after RSV MAT vaccination (RSVPreF3) or control vaccination in RSV MAT studies or from the date of current study enrollment, whichever date is earlier. The study period ends at current study enrollment for retrospective cohort participants. The study period ends at 2 years+2 months post vaccine/control for prospective cohort participants who are not pregnant at 2 years post vaccine/control. The study period ends at Day 42 post-delivery for prospective cohort participants who are pregnant at 2 years post vaccine/control or at study enrollment.

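### SAEs due to study participation or a GSK product are collected from consent in all enrolled women, but the SAP's default tabulates them only in women with a study pregnancy

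*SAP*

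**What the plan says.** **Collection.** Protocol 8.4.1 states: "All SAEs due to study participation will be collected from the signing of the ICF and/or IAF until Day 42 post-delivery or study conclusion". It adds that SAEs tied to study participation or "related to a GSK product (non-IMP) will be recorded from the time a participant consents to participate in the study". Protocol Table 2 marks this row at every contact, including the bi-annual contacts of women who are not pregnant. Prospective entry (Protocol 5.1.2) does not require a pregnancy.

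**Analysis set.** SAP 4.5 names both event categories among the other safety data, then states: "The safety analyses will be based on the Maternal Full Analysis Set and Infant Full Analysis Set, with medical records data collection", with an allowance for exceptions given elsewhere. SAP Table 2 defines the maternal FAS as "All maternal subjects who had pregnancy defined by this study". It assigns the Enrolled set, which is all consented and eligible women, to study-population summaries only. SAP 4.1 gives the FAS as the general rule for other analyses too. SAP 4.5.1 names no different set for these two categories.

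**Window.** SAP 4.5.1 plans a table of participants with at least one MAE, SAE or SAE due to study participation, counted "from study pregnancy conceived up to Day 42 post-delivery". The preferred-term table for SAEs due to study participation states no window. SAEs related to a GSK product are promised only as a maternal summary by arm, also without a window.

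**Retrospective cohort.** Under Protocol 5.1.1 these women have a pregnancy that reached Day 42 post-delivery at or before enrollment. SAP 6.2.1 says: "The study period ends at current study enrollment for retrospective cohort participants".

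**The concern.** The population in which these events are collected is not the population in which they are analysed. Collection starts at consent and does not depend on pregnancy, while analysis requires a pregnancy and medical-record data. The medical-record condition also fits poorly, since Protocol 8.4.2 prefers open verbal questioning for finding these SAEs.

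The restriction enters through the SAP. Protocol 9.3.1 puts primary and secondary analyses on the FAS, but Protocol 9.3.5 speaks only of participants for SAEs due to study participation and names no set.

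At stake are the reported percentages for SAEs attributed to study participation or to a GSK product. A programmer following the SAP would remove never-pregnant women from both numerator and denominator, although they are consented and followed for exactly these events.

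**Working it through.** **1. Reproduce the plan's expected number with a pregnancy** (inputs from Protocol 9.5 and SAP 5)

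- Women from studies in non-pregnant women: 2540 × 0.10 × 0.60 = 152.4 (stated: about 150).
- Women from studies in pregnant women: 5700 × 0.50 × 0.30 × 0.60 = 513.0 (stated: about 500).
- Total: 665.4 (stated: about 650). The difference is 2.4%, so the plan's figure reproduces.

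**2. Ceiling on the share left out**

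- Enrolled, if 60% of all 8240 enter: 8240 × 0.60 = 4944.
- In the FAS: 650 / 4944 = 13.1%.
- Outside the FAS: 4944 − 650 = 4294, which is 86.9%.

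This is an upper figure. A woman past 2 years + 2 months who has not conceived fits neither cohort, so not all of the 4294 can enroll.

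**3. Range when only a share s of the 4294 is eligible** (s is assumed; the documents do not give it)

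Omitted share = 4294s / (4294s + 650).

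| s | Never-pregnant women enrolled | Omitted share |
|---|---|---|
| 1 | 4294 | 87% |
| 1/2 | 2147 | 77% |
| 1/3 | 1431 | 69% |
| 1/5 | 859 | 57% |

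The omitted share drops below half only if fewer than 650 never-pregnant women enroll, that is s below 650 / 4294 = 15%.

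**4. Effect on precision with zero events**

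The upper 95% Clopper-Pearson limit is 1 − 0.025^(1/n). It is 0.57% at n = 650 and 0.075% at n = 4944 (the ceiling).

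**5. Window of the at-least-one table**

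- Prospective women: consented time before conception is not counted. Nor is time after Day 42, although the footnotes to Figure 2 return a woman to six-monthly contacts when Day 42 falls before 2 years + 2 months.
- Retrospective women: the pregnancy window closes at or before enrollment, while collection opens at consent. They stay in the denominator of this table with no time inside its window.
- If a share r of the FAS is retrospective, the denominator is 1 / (1 − r) times the number of women who can have a countable event: 1.11 at r = 10%, 1.33 at 25% and 2.0 at 50%. The documents do not state r; these values are assumptions.

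**The case against.** The best defence is that this is a default in a secondary safety section and that the events are not lost.

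- **The rule is qualified.** SAP 4.5 allows for exceptions and SAP 4.1 opens with a general-case phrase. But no exception is written for these events, so the default applies.
- **Other routes exist.** Every such SAE goes to the sponsor within 24 hours (Protocol 8.4.1). Disposition tables give withdrawal reasons (SAP 6.1.1), which can include an SAE or death (Protocol 7.2). SAP 6.3.1 plans maternal listings of SAEs due to study participation. A reader might infer that an event in a never-pregnant woman disappears from all output; the documents do not support that. However, withdrawal reasons show only events that led to withdrawal. The listings name no set, and the FAS default may carry over to them.
- **The window is narrow in scope.** A reader might infer that all tabulation of these events is confined to the pregnancy. It is not: the window is written for the at-least-one table of SAEs due to study participation. For the preferred-term table and the GSK-product summary, the defect is the analysis set alone.
- **Retrospective women are not wholly unobserved.** They have the enrollment contact and possible re-contact (Protocol Table 1 and its footnote c). Their time is zero only inside the pregnancy window. Changing the set does not by itself give them more time.
- **Weight.** No intervention is given (Protocol 2.3), contacts may be remote, and the protocol's own example is an accident during a contact or visit. For rare events, individual case review carries much of the information.

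The last point lowers the priority. None of the five removes the mismatch.

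**Conclusion.** The mismatch follows from the set definitions alone. As written, the planned percentages for both SAE categories exclude every enrolled woman without a study pregnancy. The at-least-one table also drops consented time outside the pregnancy window and counts retrospective women who cannot contribute to it.

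The size rests on planning figures, because the documents give neither an enrolled count nor a split by cohort. At most about 87% of enrolled women are omitted, and about 57% to 77% if one fifth to one half of never-pregnant women are eligible. A reader might take 87% as the expected value; it is a ceiling, because eligibility rules remove some never-pregnant women. The dilution from retrospective women cannot be sized, since their share is not stated.

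No primary or secondary endpoint is affected, and the events should be rare. The practical weight is modest, but the rule is wrong rather than merely incomplete, and it is cheap to correct.

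**What to change.** In SAP 4.5 and 4.5.1:

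- Tabulate SAEs due to study participation and SAEs related to a GSK product on the Enrolled set (the Enrolled Infant set for infants), without the medical-records restriction.
- Count them from consent to study conclusion.
- Present them by arm and separately by cohort, because retrospective women contribute little more than the enrollment contact.
- State that the listings of these events use the same set.
- Keep the FAS and the pregnancy-to-Day-42 window for MAEs, other SAEs and AESIs.

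The cost is SAP wording and a changed population flag for two event categories. Both sets are already defined and the data are already collected.

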4.5.1. Adverse Events

Safety analyses in maternal participants will include summaries by study arms of MAEs, SAEs, SAEs due to study participation, and SAEs related to a GSK product.

Safety analyses in infant participants will include summaries by study arms and gestational age at birth (≥ 37 weeks; <37 weeks; overall) of MAEs, SAEs and SAEs due to study participation.

For MAEs until Day 42 post-delivery (Mothers: conception to Day 42 post-delivery; Infants: birth to Day 42), the number and percentage of maternal or infant participants with each MAE with exact 95% CIs will be tabulated by study arms and displayed by Medical Dictionary for Regulatory Activities (MedDRA) preferred term. By-participant listings will be prepared.

For SAEs and SAEs due to study participation, the number and percentage of participants with each SAE with exact 95% CIs will be tabulated by study arms and by MedDRA preferred term. By-participant listings will be prepared.

The number and percentage of maternal (or infant) participants and maternal pregnancies (based on pregnancies instead of subject) reporting

- at least one MAE
- at least one SAE
- at least one SAEs due to study participation

from study pregnancy conceived up to Day 42 post-delivery (or from delivery up to Day 42 post-delivery for infant participants) with exact 95% CIs will be tabulated by study arms.

A summary of number and percentage of participants with any recorded adverse events by maximum severity will be produced.

A separate summary will be provided for study intervention (administrated from previous RSV MAT studies) related MAEs and SAEs, respectively. A study intervention-related MAE (or SAE) is defined as a MAE (or SAE) for which the investigator classifies the possible relationship to study intervention from previous RSV MAT studies as “Yes”. A worst-case scenario approach will be taken to handle missing relatedness data, i.e. the summary table will include events with the relationship to study intervention as ‘Yes’ or missing.

Summaries of life-threatening and fatal SAEs by PT will also be created.

By participant listings of MAEs, SAEs and SAEs due to study participation will be prepared.

4.5.1.1. COVID-19 Assessment and COVID-19 AEs

Maternal and infant COVID-19 cases identified during the study (as per standard of care) will be captured from patient self-report. Additionally, COVID-19 cases documented in medical records will be reported as medically-attended AE or SAE according to standard criteria, as outlined in the protocol Section 10.2.

A participant is defined as having a suspected, probable or confirmed COVID-19 infection during the study if the answer is “Confirmed”, “Probable” or “Suspected” to the case diagnosis question from the COVID-19 coronavirus infection assessment electronic Case Report Form (eCRF).

Numbers and percentage of participants with a suspected, probable or confirmed COVID-19 infection will be summarized by study arms.

Number and percentage of participants who had a COVID-19 test performed and number and percentage of participants with positive, negative and indeterminate results will be summarized by study arms.

Number and percentage of participants who had COVID-19 test positive will be summarized by severity and study arms. The severity definition is adapted from the CDC of US [[CDC](#), 2022].

- Asymptomatic: test positive for COVID but have no symptoms
- Mild: have COVID symptoms, but not moderate or severe (as defined below)
- Moderate: experienced shortness of breath or had difficulty breathing
- Severe: were hospitalized

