- An *uncomplicated* vaginal delivery or planned cesarean section *expected* to occur in a hospital setting should NOT be reported as an AE, MAE or SAE.
- A medical *complication* that requires a cesarean section or an emergency induction may be reported as an SAE/AESI (as applicable), using the corresponding Expedited AE report form.

8.4.8.2. Reporting of congenital anomalies in relation to pregnancy outcomes and SAEs and/or AESIs

Table 9 summarizes the requirements for AESI/SAE reporting of adverse pregnancy outcomes when congenital anomalies are/are not present.

Table 9 Reporting pregnancy outcomes with or without congenital anomalies as AESIs and/or SAEs

	Live birth		Fetal death /stillbirth		Elective / Therapeutic Termination	
	AESI	SAE	AESI	SAE	AESI	SAE
None	-	-	-	X	-	X
Major ¹	X	if reportable per MACDP ³	-	X	-	X
Minor ²	-	if reportable per MACDP ³	-	X	-	X

* In the event of infant's participation in the study, congenital anomalies are to be reported in the infant's eCRF.

However, when there is no live birth, or no signed informed consent for the infant or the congenital anomaly is being reported for a subsequent pregnancy, it will be encoded in the maternal participant's eCRF.

¹Structural or functional defects that require surgical and/or medical treatment and that have serious adverse effects on health or development (functional) or have significant cosmetic impact.

²Anatomic variants or defects that do not have serious medical, functional or cosmetic consequences for the child.

³Metropolitan Atlanta Congenital Defects Program (MACDP) 6-Digit Code Defect List

Additional guidance when congenital anomalies are present are as follows:

The term “congenital anomaly” is broad. GSK uses the case definitions provided in the Centers for Disease Control and Prevention (CDC) Metropolitan Atlanta Congenital Defects Program guidelines, with specific reference to the MACDP 6-Digit Code Defect List [MACDP, 2021] to ensure that the collection and recording of these data is complete and consistent across studies and projects.

To report a pregnancy outcome of live birth with congenital anomaly as an SAE per these guidelines, an infant must have a birth defect that is *included in MACDP surveillance data* per the MACDP 6-Digit Code Defect List. (Congenital anomalies that are not included in MACDP surveillance data may be reported as medically attended or serious adverse events, if appropriate).

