8.4.10. Covid-19 Infection

Maternal and infant COVID-19 cases identified during the study (as per standard of care) will be captured and reported using standard medically attended AE or SAE criteria, as outlined in Section 10.2. Additionally, all reported COVID-19 infections during a study pregnancy will be captured and reported on a COVID-19 screen of the eCRF.

COVID-19 cases should be reported in the eCRF according to the WHO Case Definition [[WHO, 2022](#)] using one of the following terms:

- Suspected COVID-19 infection
- Probable COVID-19 infection
- Confirmed COVID-19 infection.

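### The SAP grades a positive COVID-19 test as Severe on hospitalization alone, so a symptom-free mother or newborn in hospital for a birth can meet both Severe and Asymptomatic.

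*SAP*

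**What the plan says.** SAP 4.5.1.1 covers mothers and infants: "Maternal and infant COVID-19 cases identified during the study (as per standard of care) will be captured from patient self-report". It plans this output: "Number and percentage of participants who had COVID-19 test positive will be summarized by severity and study arms". The scale, which the SAP says is adapted from a US CDC source, has four grades:

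- The lowest grade depends only on the absence of symptoms: "Asymptomatic: test positive for COVID but have no symptoms".
- The second is the only one that rules out other grades: "Mild: have COVID symptoms, but not moderate or severe (as defined below".
- The third rests on breathing alone and does not rule out inpatients: "Moderate: experienced shortness of breath or had difficulty breathing".
- The top grade is given in three words: "Severe: were hospitalized".

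Nothing more is said about the reason for admission, its timing relative to the test, or which grade applies when two are met.

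Protocol 8.4.10 sets the scope of collection for the pregnancy: "all reported COVID-19 infections during a study pregnancy will be captured and reported on a COVID-19 screen of the eCRF". It names three levels of case certainty (suspected, probable, confirmed) but no severity rule. Protocol 8.4.8.1 says that an uncomplicated vaginal delivery or planned cesarean in hospital "should NOT be reported as an AE, MAE or SAE".

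**The concern.** Hospitalization can mark severe disease where admission is otherwise unusual. Here it is part of expected care. Most women graded will be observed up to and through a delivery, and an infant born in hospital starts life there. The protocol recognizes this for adverse events by setting uncomplicated hospital delivery aside. The COVID-19 severity rule has no matching exception.

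Two things follow. A positive test found during a delivery or birth stay can raise the count of severe COVID-19 with no severe illness behind it. And because the grades overlap, two programmers could produce different tables from the same data while both following the SAP. At stake is whether this table describes COVID-19 severity by arm. Severe counts are likely to be small, so a few such cases could change how the table reads.

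**Working it through.** The plan gives no figure to reproduce, and no sample size or error rate is involved. The check applies the four definitions literally.

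**Inputs (all from SAP 4.5.1.1).** For a test-positive participant let S = COVID-19 symptoms, D = breathing difficulty, H = hospitalized. D is taken to imply S, which leaves six combinations. The rules are: Asymptomatic if not S; Moderate if D; Severe if H; Mild if S and neither D nor H. Only Mild excludes other grades.

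| S | D | H | Grades met as written |
|---|---|---|---|
| no | no | no | Asymptomatic |
| no | no | yes | Asymptomatic and Severe |
| yes | no | no | Mild |
| yes | no | yes | Severe |
| yes | yes | no | Moderate |
| yes | yes | yes | Moderate and Severe |

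Two of six combinations meet two grades. The fourth row meets only one, but it can still mislead: a woman with mild symptoms who is in hospital only to deliver is Severe, because Mild gives way to Severe.

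**A highest-grade rule on its own.** The overlaps disappear, but the symptom-free woman in labor is then placed in Severe. That rule alone makes the main problem worse.

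**A link to COVID-19 plus a highest-grade rule.** Let H mean hospitalized because of COVID-19. A delivery or birth stay alone then gives H = no, so the participant is Asymptomatic, Mild or Moderate according to symptoms. All six combinations map to one grade.

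**Illustration of sensitivity (assumed rates only).** Suppose 5% of test-positive mothers are truly admitted for COVID-19 and, independently, a share d has a delivery admission that counts. The share meeting Severe is 1 − (1 − 0.05)(1 − d):

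- d = 5%: 1 − 0.95 × 0.95 = 9.8%
- d = 25%: 1 − 0.95 × 0.75 = 28.8%
- d = 50%: 1 − 0.95 × 0.50 = 52.5%
- d = 95%: 1 − 0.95 × 0.05 = 95.3%

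The spread shows only that the result depends almost entirely on which admissions are counted. It does not estimate what will happen.

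**The case against.** The best reply is that the line should be read in context. It is one item of a COVID-19 scale, applied to people with a positive test. The Moderate line does not tie breathlessness to COVID-19 either, yet nobody would read it as breathlessness from any cause. The data come from a dedicated COVID-19 eCRF form that is not in the documents. If its hospitalization item asks about admission for the infection, the problem is solved at source. The protocol already separates expected delivery stays from event-driven admissions in Sections 8.4.8.1 and 10.2.2, and severe COVID-19 events will also appear in SAE tables that do not use this scale. Nor do the documents say that women or newborns are routinely tested on admission; cases are those found under standard care.

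Much of this stands as a limit on size. It does not remove the defect. The form may help, but the SAP is where the rule is set and it does not say so. Context does not settle which grade a symptom-free inpatient receives. SAP 4.5.1 uses maximum severity for adverse events generally, but does not carry that into this table.

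Three stronger readings are tempting, and the documents do not support them:

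- **Almost every test-positive woman who delivers in hospital will be graded Severe.** This requires linking, say, a week-39 delivery to a week-10 infection. The SAP sets no time window, but it does not instruct that link.
- **The preterm-birth risk-factor work is damaged.** SAP 4.3.2.2 lists COVID infection during pregnancy as yes/no, so the severity grade does not enter.
- **The table's percentages will exceed 100%.** They could, on the literal text. But the Mild wording suggests an ordered scale, and the programming may impose one.

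**Conclusion.** The point holds as a definitional defect of minor consequence. As written, Severe can be met through a hospital stay unrelated to COVID-19, and two of six combinations satisfy two grades. It is safe to say that symptom-free cases *can* be counted as Severe. It is not safe to say that they will be, because the SAP does not say which grade prevails and the eCRF question is unseen.

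The effect is confined to the descriptive table of positive tests by severity and arm. No primary endpoint, secondary endpoint or listed risk factor uses the grading, and the outputs planned for the safety review team in SAP 6.3.2 include no such table. The size of the misgrading cannot be derived from the documents.

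For newborns there is one further assumption: that the birth stay is recorded as hospitalization of the infant, which the documents do not state.

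**What to change.** In SAP 4.5.1.1:

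1. Define Severe, for this table, as hospitalized because of COVID-19. State that admission for labor or delivery, or the birth stay, does not count on its own.
2. Assign each test-positive participant to the single highest grade met. Adopt this together with item 1, not in its place.
3. Take the reason for admission from the COVID-19 eCRF screen or the medical record where available. The MAE or SAE record is not enough: cases come from self-report, and under the footnote to Protocol Table 1 an event noted incidentally in routine care is not counted as medically attended. A symptom-free positive may therefore have no such record.
4. List cases whose reason for admission is unknown separately.

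The cost is a short wording change and a small programming change. The downside is that a few cases may have an unknown reason. If the eCRF already asks about admission for COVID-19, items 1 and 3 only write down what is collected.
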